### 6.3.2 Response Criteria for Lymphoma – PCNSL

The following response criteria as per the CNS lymphoma working group (Abrey et al. JCO 2005) will be used for subjects on study with PCNSL:

Response	Brain Imaging	Corticosteroid dose	Eye examination	CSF cytology
CR	No contrast enhancement	None	Normal	Negative
CRu	No contrast enhancement	Any	Normal	Negative
	Minimal abnormality	Any	Minor RPE abnormality	Negative
PR	50% decrease in enhancing tumor	Irrelevant	Minor RPE abnormality or normal	Negative
	No contrast enhancement	Irrelevant	Decrease in vitreous cells or retinal infiltrate	Persistent or suspicious
PD	25% increase in lesion	Irrelevant	Recurrent or new ocular disease	Recurrent or positive
	Any new site of disease: CNS or systemic			

Abbreviations: CR, complete response; CRu, unconfirmed complete response; RPE, retinal pigment epithelium; PR, partial response; PD, progressive disease

### 6.3.3 Best Overall Response

The best overall response is the best response recorded from the start of the treatment until disease progression/recurrence (taking as reference for progressive disease the smallest measurements recorded since the treatment started). The patient's best response assignment will depend on the achievement of both measurement and confirmation criteria.

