### **3.5 TREATMENT CONSIDERATIONS/EXCEPTIONS**

#### **3.5.1 Treatment Beyond Progression (“Pseudo-progression”)**

A minority of patients treated with immunotherapy may derive clinical benefit despite initial evidence of progressive (PD). Patients suspected to have PD by response criteria will be permitted to continue pembrolizumab treatment beyond confirmed PD as measured by the appropriate evaluation criteria as long as they meet all of the following criteria as determined by the investigator:

- Investigator assessed clinical benefit
- Subject is tolerating pembrolizumab
- Stable performance status
- Absence of other signs and symptoms indicating disease progression
- Absence of evidence to suggest that other or alternative medical intervention or treatment is needed to treat the disease

Patients that meet the above criteria should have repeat radiographic evaluation within 6 weeks of initial investigator-assessed progression to determine whether there has been a decrease in the tumor size or continued PD.

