### **3.6 TREATMENT DISCONTINUATION/POST-TREATMENT EVALUATIONS**

Taking into account required 30-Day Safety and Follow-Up requirements below (Section 3.7), the following will be performed at the end of treatment (and at disease progression, if subject discontinues treatment for a reason other than progression) within 30 days of the last dose of trial treatment (and prior to the start of new anti-cancer therapy).

In absence of progression or new anti-cancer therapy, follow-up will continue at the following time points, unless otherwise noted: every 3 months (+/- 2 weeks) for first year after completion of therapy, every 6 months for years 2-5 (+/- 4 weeks), and then annually thereafter (+/- 6 weeks) at the discretion of the investigator. Other assessments should be performed as clinically indicated; see Study Calendar (Section 3.8) for additional information.

Upon disease progression or initiation of other anti-cancer therapy, contact will be for survival only until the subject is off study; unless otherwise clinically indicated.

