## 3.7 FOLLOW-UP EVALUATIONS

The investigator or qualified designee will review all new anti-neoplastic therapy initiated after the last dose of trial treatment. If a subject initiates a new anti-cancer therapy within 30 days after the last dose of trial treatment, the 30-day Safety Follow-up visit must occur before the first dose of the new therapy.

Once new anti-cancer therapy has been initiated the subject will move into survival follow-up.

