### 3.7.3 Follow-Up Visits – Survival/Post-Disease Progression

Once a subject experiences confirmed disease progression or starts a new anti-cancer therapy, the subject moves into the survival follow-up phase and should be contacted approximately every 12 weeks to assess for survival status until death, withdrawal of consent, or the end of the study, whichever occurs first (see [Study Calendar](#)).

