#### **3.10.1 Criteria for Removal from Protocol Therapy**

- Completed 24 months or more of uninterrupted treatment with pembrolizumab without disease progression per Section [3.5.2.1](#) at the discretion of the treating investigator/subject. **NOTE:** Patients may be eligible for up to one year of additional study treatment if they progress after stopping study treatment provided they meet the requirements detailed in Section [3.5.3](#).
- Achieved a complete response (CR) and completed at least 1 year of treatment with pembrolizumab per Section [3.5.2.2](#) at the discretion of the treating investigator/subject. **NOTE:** Patients may be eligible for up to one year of additional study treatment if they progress after stopping study treatment provided they meet the requirements detailed in Section [3.5.3](#).
- Confirmed radiographic disease progression
  - A subject may be granted an exception to continue on treatment with confirmed radiographic progression if clinically stable or clinically improved, please see Section [3.5.1](#).
- Unacceptable toxicity as listed in Section [3.3.2](#).
- Intercurrent illness that prevents further administration of treatment
- Requirement for use of prohibited therapies as listed in Section [4.2](#)
- Pregnancy
- Subject's requests to be withdrawn from protocol therapy
- Noncompliance with trial treatment or procedure requirements
- Investigator's decision to withdraw the subject
- Study is cancelled for any reason

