### 4.2 PROHIBITED MEDICATIONS

Patients are prohibited from receiving the following therapies during the Screening and Treatment Phase (including retreatment for post-complete response relapse) of this trial:

- Antineoplastic systemic chemotherapy or biological therapy
- Immunotherapy not specified in this protocol
- Chemotherapy not specified in this protocol
- Investigational agents other than pembrolizumab
- Radiation therapy
  - **NOTE:** Radiation therapy to a symptomatic solitary lesion or to the brain may be allowed at the investigator's discretion.
- Live vaccines within 30 days prior to the first dose of trial treatment and while participating in the trial. Examples of live vaccines include, but are not limited to, the following: measles, mumps, rubella, varicella/zoster, yellow fever, rabies, BCG, and typhoid vaccine.
- Systemic glucocorticoids for any purpose other than to modulate symptoms from an event of clinical interest of suspected immunologic etiology are generally not allowed. For subjects who are on stable doses of steroids (i.e.,  $\leq 10$  mg/day of dexamethasone or

equivalent) at study entry, the investigator should try to taper/discontinue dosing after initiation of therapy, if appropriate. Other exceptions include the use of physiologic doses of corticosteroids and steroid use for acute issues (e.g., for up to 2 weeks unless otherwise felt to be clinically necessary in the opinion of the PI to continue for longer) after consultation with the PI.

Patients who, in the assessment by the investigator, require the use of any of the aforementioned treatments for clinical management should be removed from the trial. Patients may receive other medications that the investigator deems to be medically necessary.

The Exclusion Criteria describes other medications which are prohibited in this trial.

There are no prohibited therapies during the Post-Treatment Follow-up Phase.

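### A response first recorded after permitted on-treatment radiation can count towards the primary ORR, because the best-response window in 6.3.3 closes only at progression

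*Combined protocol and SAP*

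**What the plan says.** The primary endpoint is ORR, assessed at up to 24 months (9.1) and reported per cohort with a 95% confidence interval (9.4.2). Section 6.3.3 defines the window: "The best overall response is the best response recorded from the start of the treatment until disease progression/recurrence". The only further condition there is that measurement and confirmation criteria are met.

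Section 4.2 lists radiation among the therapies prohibited during screening and treatment, then makes an exception: "Radiation therapy to a symptomatic solitary lesion or to the brain may be allowed" at the investigator's discretion. Patients on treatment continue to be imaged after cycles 2 and 6, at months 9, 12 and 18, and every 6 months thereafter (3.4.3).

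Other passages bear on what happens to an irradiated patient:

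- 4.2 also says that patients who "require the use of any of the aforementioned treatments for clinical management should be removed from the trial".
- 3.10.1 lists as a reason to stop protocol therapy: "Requirement for use of prohibited therapies as listed in Section" 4.2.
- 3.6: "Upon disease progression or initiation of other anti-cancer therapy, contact will be for survival only until the subject is off study".
- 3.7: "Once new anti-cancer therapy has been initiated the subject will move into survival follow-up".
- 3.7.3: once a patient has confirmed progression or "starts a new anti-cancer therapy, the subject moves into the survival follow-up phase".
- 3.5.1 makes continuation beyond progression conditional on, among other things: "Absence of evidence to suggest that other or alternative medical intervention or treatment is needed to treat the disease".

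Radiation is dealt with explicitly in one endpoint only. EFS (6.3.6) counts alternative lymphoma therapy, with radiation as its example, as an event.

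**The concern.** The trial has no control group, so every counted response is attributed to pembrolizumab. The exception covers the brain and solitary symptomatic lesions, either of which may be a patient's only site of disease. Section 1.2.3 itself acknowledges that radiotherapy produces remissions in PCNSL, if short ones, and 9.2 plans for PCNSL to make up 10 of the 20 patients in the extranodal DLBCL cohort. A patient could have an EFS event on the day of radiation and then become an ORR responder because of that radiation.

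At stake is whether the primary ORR measures the activity of pembrolizumab or, in some patients, that of pembrolizumab plus radiation.

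**Working it through.** **1. Is there a cut-off anywhere?** The places where one could stand are:

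| Section | Content | Rule for radiation? |
|---|---|---|
| 6.3.1, 6.3.2 | Response tables | None (the PCNSL table considers steroid dose, not radiation) |
| 6.3.3 | Window from start of treatment to progression | None |
| 6.3.7, 9.3 | Evaluability: two doses and a follow-up scan | None |
| 9.1, 9.4.2 | ORR up to 24 months, 95% CI | None |
| 6.3.6 | EFS | Radiation is an event |

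**2. How wide is the exposed window?** Four things must coincide: radiation under the exception before documented progression, no earlier response, continued pembrolizumab, and a later scan that meets response criteria. Radiation after progression falls outside the window by 6.3.3 itself.

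**3. Reproduce the design (9.2).** Inputs: 20 evaluable patients per cohort, exact binomial test, one-sided 0.10. The minimum passing count k is the smallest with P(X ≥ k | null) ≤ 0.10.

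- GZL, 50% vs 80%: k = 14, error 0.0577, power 0.913 (stated 91%). At k = 13 the error would be 0.132.
- Extranodal DLBCL, 40% vs 70%: k = 12, error 0.0565, power 0.887 (stated 88%). At k = 11 the error would be 0.128.

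The one-sided 90% bounds also match: 53.3% and 83.4% for 14/20; 43.3% and 75.1% for 12/20.

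**4. Effect on the estimate.** One response due only to radiation adds 1/20 = 5 percentage points to a cohort ORR and 1/10 = 10 points to the planned PCNSL estimate.

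**5. Effect on the chance of a false pass.** The documents give no radiation rate, so r = 1 to 3 per cohort is an assumption. Fix r patients as responders through radiation alone and let the other 20 − r respond at the null rate p0:

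P(pass) = P(Y ≥ k − r), with Y ~ Bin(20 − r, p0)

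| Rule | r = 0 | r = 1 | r = 2 | r = 3 |
|---|---|---|---|---|
| Extranodal DLBCL, 12/20, p0 = 40% | 5.7% | 8.8% | 13.5% | 19.9% |
| GZL, 14/20, p0 = 50% | 5.8% | 8.4% | 11.9% | 16.6% |

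**6. Same check with the planned 95% interval.** Exact (Clopper-Pearson) lower limits are 36.1% for 12/20, 40.8% for 13/20, 45.7% for 14/20 and 50.9% for 15/20. The lowest counts that exclude the null are therefore 13/20 (above 40%) and 15/20 (above 50%).

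| Rule | r = 0 | r = 1 | r = 2 | r = 3 |
|---|---|---|---|---|
| Extranodal DLBCL, 13/20 | 2.1% | 3.5% | 5.8% | 9.2% |
| GZL, 15/20 | 2.1% | 3.2% | 4.8% | 7.2% |

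**7. A harsher model.** Suppose instead that all 20 patients respond to the drug at the null rate and r drug non-responders are then converted by radiation. P(pass) becomes P(X ≥ k − r) with X ~ Bin(20, p0). For r = 1, 2, 3 this gives 12.8%, 24.5%, 40.4% (12/20) and 13.2%, 25.2%, 41.2% (14/20).

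**The case against.** The strongest reply is that such patients leave the trial or stop being assessed. Section 4.2's removal sentence and 3.10.1 could end therapy, and 3.6, 3.7 and 3.7.3 could move the patient to survival contact only. This limits how often the problem could arise, but it does not close the gap. If the removal sentence covered the excepted radiation, the exception would have little effect. Section 3.10.1 points back to 4.2, which contains the exception. Sections 3.6 and 3.7 are written for the period after treatment. Section 3.7.3 is worded more broadly but does not say whether excepted radiation is a new anti-cancer therapy. None of them amends 6.3.3 or Section 9.

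The magnitude is assumed, and this stands. Nothing in the documents supports any particular r. In the step 5 model the average drug-only response rate is also below the null (38%, 36% and 34% in extranodal DLBCL; 47.5%, 45% and 42.5% in GZL), so the figures are not error rates at a true 40% or 50%. That makes them the milder of the two models. Under it one radiation response does not breach 0.10 but two do; under the harsher model one is enough. The GZL figures have less support, since the brain exception mainly concerns PCNSL.

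It is also true that 9.2 presents 14/20 and 12/20 as illustrations and that 9.4.2 plans an estimate with an interval, with no go/no-go rule. The shift of 5 points per response does not depend on any such rule.

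Finally, excluding post-radiation responses might seem to clash with the DOR definition. It does not: 1.1.2 restricts DOR to patients who respond, so the DOR set follows the ORR definition. DOR in a patient who responds before radiation would still run through it; the change proposed here does not address that.

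**Conclusion.** The concern holds. Followed literally, 6.3.3 lets a response first recorded after permitted radiation, before documented progression, count towards the primary ORR. Sections 4.2, 3.10.1, 3.6, 3.7 and 3.7.3 do not settle whether that situation can arise.

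The size is 5 percentage points per such response in a 20-patient cohort and 10 points in the planned PCNSL group. Under the milder model, with 1 to 3 such patients assumed, the chance of a false pass rises from just under 6% to between 8.8% and 19.9% in extranodal DLBCL and between 8.4% and 16.6% in GZL. All figures assume the planned 20 per cohort; 11.2 records early closure to accrual, so actual numbers may differ, and with fewer patients each response weighs more. The window is narrow and the radiation rate unknown, so this is a change that should be made, held with medium confidence.

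**What to change.** State in 6.3.3 and 9.4.2 that:

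- only responses documented before any radiation or other non-protocol anti-lymphoma therapy count towards best overall response and ORR;
- evaluable patients without such a response stay in the denominator as non-responders;
- ORR including post-radiation responses is reported as a sensitivity analysis.

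Leave the PFS and DOR definitions as they are; EFS already counts radiation. Separately, reconcile the radiation exception in 4.2 with that section's removal sentence and with 3.10.1, 3.6, 3.7 and 3.7.3, so that it is clear whether treatment and disease assessment continue after excepted radiation. No view is taken on whether radiation should be permitted.

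The cost is about two sentences of analysis wording. Radiation dates are already needed for EFS. ORR may come out slightly lower, including where unirradiated sites respond later; the sensitivity analysis shows that case.

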### 6.3.4 Duration of Response

The duration of response (DOR) is measured from the time measurement criteria are met for CR or PR (whichever is first recorded) until the first date that recurrent or progressive disease is objectively documented (taking as reference for progressive disease the smallest measurements recorded since the treatment started), death, or, in the absence of PD, date of last assessment.

### 6.3.5 Progression-Free Survival

Progression-free survival (PFS) is defined as the duration of time from the date of study enrollment until time of disease relapse, disease progression, or death, whichever occurs first.

### 6.3.6 Event-Free Survival

Event-free survival (EFS) is defined as the duration of time from the date of study enrollment until time of disease relapse, disease progression, alternative therapy for lymphoma given (such as radiation), or death, whichever occurs first.

### 6.3.7 Other

Evaluable for toxicity: All patients who receive at least 1 dose of pembrolizumab will be evaluable for toxicity.

**Evaluable for objective response:** Only those patients who have measurable or evaluable disease present at baseline, have received at least two doses of therapy, and have had their disease re-evaluated with radiographic imaging will be considered evaluable for response. These patients will have their response classified according to the definitions stated below. (NOTE: Patients who exhibit objective disease progression prior to the end of cycle 1 will also be considered evaluable.)

#### **6.4 TOXICITY CRITERIA**

The following adverse event management guidelines are intended to ensure the safety of each patient while on the study. The descriptions and grading scales found in the revised NCI Common Terminology Criteria for Adverse Events (CTCAE) version 4.0 will be utilized for AE reporting. All appropriate treatment areas should have access to a copy of the CTCAE version 4.0. A copy of the CTCAE version 4.0 can be downloaded from the CTEP web site ([http://ctep.cancer.gov/protocolDevelopment/electronic\\_applications/ctc.htm#ctc\\_40](http://ctep.cancer.gov/protocolDevelopment/electronic_applications/ctc.htm#ctc_40)).

### **7 NIH REPORTING /DATA AND SAFETY MONITORING PLAN**

#### **7.1 DEFINITIONS**

##### **7.1.1 Adverse Event**

Please refer to definitions provided in Policy 801: Reporting Research Events found [here](#).

#### **7.2 OHSRP OFFICE OF COMPLIANCE AND TRAINING / IRB REPORTING**

##### **7.2.1 Expedited Reporting**

Please refer to the reporting requirements in Policy 801: Reporting Research Events and Policy 802 Non-Compliance Human Subjects Research found [here](#).

##### **7.2.2 IRB Requirements for PI Reporting at Continuing Review**

Please refer to the reporting requirements in Policy 801: Reporting Research Events found [here](#).

#### **7.3 NCI CLINICAL DIRECTOR REPORTING**

Problems expeditiously reported to the OHSRP in iRIS will also be reported to the NCI Clinical Director. A separate submission is not necessary as reports in iRIS will be available to the Clinical Director.

In addition to those reports, all deaths that occur within 30 days after receiving a research intervention should be reported via email to the Clinical Director unless they are due to progressive disease.

To report these deaths, please send an email describing the circumstances of the death to [name] at [[contact]](mailto:[contact]) within one business day of learning of the death.

#### **7.4 NIH REQUIRED DATA AND SAFETY MONITORING PLAN**

##### **7.4.1 Principal Investigator/Research Team**

The clinical research team will meet on a regular basis (i.e., approximately weekly) when patients are being actively treated on the trial to discuss each patient. Decisions about trial continuation will be made based on the efficacy data from prior patients at appropriate time points per the statistical plan.

All data will be collected in a timely manner and reviewed by the principal investigator or a lead associate investigator. Events meeting requirements for expedited reporting as described in section **7.2.1** will be submitted within the appropriate timelines.

The principal investigator will review adverse event and response data on each patient to ensure safety and data accuracy. The principal investigator will personally conduct or supervise the investigation and provide appropriate delegation of responsibilities to other members of the research staff.

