## **9.2 SAMPLE SIZE DETERMINATION**

The trial will be conducted in two cohorts using a single stage design for evaluating efficacy in each cohort since modestly high clinical response rates are expected in both cohorts.

In the GZL cohort, results from a prior study indicate that 3 of 3 patients had a complete response when treated with (authors data, manuscript accepted for publication). With 20 evaluable patients, there would be 91% power to rule out 50% and be consistent with 80% who may be able to experience a clinical response, using an exact binomial test with a 0.10 one-sided significance level. As an illustration, if 20 evaluable patients are enrolled, 14 of 20 (70.0%) who experience a clinical response would have an associated one-sided lower 90% confidence interval bound of 53.3%, and simultaneously an associated one-sided upper 90% confidence interval bound of 83.4%. This demonstrates that 14 responses in 20 patients would be a desirable result based on the parameters selected.

In the PCNSL and extranodal DLBCL cohort, newly published results in 5 patients suggest the overall response rate will be moderately high. With 20 evaluable patients, there would be 88% power to rule out 40% and be consistent with 70% who may be able to experience a clinical response, using an exact binomial test with a 0.10 one-sided significance level. As an illustration, if 20 evaluable patients are enrolled, 12 of 20 (60.0%) who experience a clinical response would have an associated one-sided lower 90% confidence interval bound of 43.3%, and simultaneously an associated one-sided upper 90% confidence interval bound of 75.1%. This demonstrates that 12 responses in 20 patients would be a desirable result based on the parameters selected.

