#### 9.4.5 Planned Interim Analyses

No interim analyses are planned because of the single stage design of the trial.

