## **12 REGULATORY AND OPERATIONAL CONSIDERATIONS**

### **12.1 STUDY DISCONTINUATION AND CLOSURE**

This study may be temporarily suspended or prematurely terminated if there is sufficient reasonable cause. Written notification, documenting the reason for study suspension or termination, will be provided by the suspending or terminating party to study participants, investigator, funding agency, and regulatory authorities. If the study is prematurely terminated or suspended, the Principal Investigator (PI) will promptly inform study participants, the Institutional Review Board (IRB), and sponsor and will provide the reason(s) for the termination or suspension. Study participants will be contacted, as applicable, and be informed of changes to study visit schedule.

Circumstances that may warrant termination or suspension include, but are not limited to:

- Determination of unexpected, significant, or unacceptable risk to participants
- Demonstration of efficacy that would warrant stopping
- Insufficient compliance to protocol requirements
- Data that are not sufficiently complete and/or evaluable
- Determination that the primary endpoint has been met
- Determination of futility

Study may resume once concerns about safety, protocol compliance, and data quality are addressed, and satisfy the sponsor and IRB.

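### Does the monitoring plan's reference to efficacy-based continuation decisions undermine the single-stage design?

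*Combined protocol and SAP*

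**What the plan says.** Section 7.4.1, on the role of the principal investigator and research team, says: "Decisions about trial continuation will be made based on the efficacy data from prior patients at appropriate time points per the statistical plan". The same section provides for roughly weekly team meetings and adds that "The principal investigator will review adverse event and response data on each patient", for the stated purposes of safety and accurate data.

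The statistical section reads differently. Section 9.2 describes the trial as "using a single stage design for evaluating efficacy in each cohort", with 20 evaluable patients per cohort and power computed "using an exact binomial test with a 0.10 one-sided significance level". Section 9.4.5 states: "No interim analyses are planned because of the single stage design of the trial". Sections 9.4.1 and 9.4.2 plan to report the response rate in each cohort with a 95% confidence interval. They give no rejection rule.

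Section 12.1 lists circumstances that might justify suspending or ending the study. Three concern efficacy: "Demonstration of efficacy that would warrant stopping", "Determination that the primary endpoint has been met" and "Determination of futility". None has a threshold or a time point. Section 11.2 records that accrual was closed early and mentions this together with poor recruitment.

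**The concern.** Section 7.4.1 points to decision times that section 9 does not contain and says are not planned. The trial is open-label, the principal investigator sees each patient's response, and section 8.1.5 has that person monitor aggregate efficacy events. Accrual did stop early. A reader may therefore ask whether the number of patients depended on the responses seen so far.

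That matters for the test in 9.2. An exact binomial test keeps its level at whatever sample size is reached, provided the size was not chosen by looking at the responses. If the team had stopped at the first look that met the 0.10 criterion, the overall chance of wrongly ruling out 50% (gray-zone cohort) or 40% (extranodal cohort) could exceed 10%.

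**Working it through.** **1. The plan's own figures.** Inputs from 9.2: n = 20 per cohort, one-sided level 0.10, null and target rates 50% and 80% (gray-zone), 40% and 70% (extranodal). The critical count r is the smallest r for which P(X ≥ r | n = 20, p0) ≤ 0.10.

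- Gray-zone: P(X ≥ 13 | 0.5) = 0.1316, too large; P(X ≥ 14 | 0.5) = 0.0577, so r = 14. Power = P(X ≥ 14 | 0.8) = 0.9133 (stated 91%).
- Extranodal: P(X ≥ 11 | 0.4) = 0.1275, too large; P(X ≥ 12 | 0.4) = 0.0565, so r = 12. Power = P(X ≥ 12 | 0.7) = 0.8867 (stated 88%, which truncates rather than rounds).
- Exact one-sided 90% bounds: 53.3% and 83.4% for 14/20; 43.3% and 75.1% for 12/20. All four match 9.2.

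Every figure describes a single analysis at n = 20.

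**2. The passages side by side.** Section 7.4.1 makes continuation decisions at times taken from the statistical plan. Section 9.2 has one stage and 9.4.5 has no interim analysis, so the set of times is empty. The sentence is a cross-reference with nothing at the other end. It does not compete with 9.4.5, because it hands the timing to section 9. Section 12.1 says what might justify stopping and schedules nothing.

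**3. What unplanned looks would cost.** The documents give no look times, so those below are assumptions. The 9.2 criterion is applied at each look, with stopping at the first success. For one extra look at m patients:

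type I error = P(X_m ≥ r_m | p0) + P(X_m < r_m and X_20 ≥ r_20 | p0).

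| Cohort | m | r_m | At the look | Added at n = 20 | Total |
|---|---|---|---|---|---|
| Gray-zone | 9 | 7 | 0.0898 | 0.0282 | 0.1180 |
| Gray-zone | 10 | 8 | 0.0547 | 0.0342 | 0.0889 |
| Gray-zone | 15 | 11 | 0.0592 | 0.0220 | 0.0812 |
| Gray-zone | 18 | 13 | 0.0481 | 0.0177 | 0.0658 |
| Extranodal | 7 | 5 | 0.0963 | 0.0304 | 0.1267 |
| Extranodal | 10 | 7 | 0.0548 | 0.0330 | 0.0877 |
| Extranodal | 15 | 9 | 0.0950 | 0.0121 | 0.1071 |
| Extranodal | 18 | 11 | 0.0576 | 0.0123 | 0.0700 |

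Totals come from unrounded terms, so the last digit can differ. Over every single extra look from m = 5 to 19, the lowest and highest totals are those at m = 18 and m = 9 (gray-zone) and at m = 18 and m = 7 (extranodal).

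The same patient-by-patient recursion with more looks gives (gray-zone / extranodal):

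- looks at 10, 15 and 20: 0.1019 / 0.1212;
- looks at 12, 16 and 20: 0.1005 / 0.0956;
- a look after each patient from 10 to 20: 0.1397 / 0.1636.

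The counts are discrete, so the result depends on when the looks fall as well as on how many there are. One look can exceed 10%, and three can stay below it.

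**4. A futility-only look.** Suppose the trial stops at n = 10 with 5 or fewer responses (gray-zone) or 4 or fewer (extranodal), and otherwise tests at 20. Type I error falls to 0.0548 / 0.0531. Power moves from 0.9133 to 0.9028 and from 0.8867 to 0.8712.

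**5. Closure for recruitment.** If accrual stops for reasons unrelated to response, the exact criterion at the achieved n still holds its level. At n = 10 (an assumed value) the level is 0.0547 / 0.0548 and power is 0.678 / 0.650. Such a closure costs power, and the type I error stays within 10%.

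**The case for a change.** The strongest case for a change is that a protocol should not contain two statements about interim decisions that a reader has to reconcile. Section 12.1 adds three efficacy-related grounds for stopping without boundaries, cumulative responses were visible to the person running the trial, and accrual did end before plan. If responses influenced that decision, neither the 0.10 test nor the nominal coverage of the 95% interval would be assured. Deleting one sentence costs almost nothing.

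The inconsistency itself stands. So does the arithmetic: even one unadjusted look can take the error above 10%. What does not stand is the step from loose wording to a flawed analysis. Nothing in the documents defines or records an efficacy look. The response review in 7.4.1 is for safety and data accuracy, and the aggregate monitoring in 8.1.5 is for patient safety. Section 12.1 is a permissive list rather than a schedule. The reason given in 11.2 concerns recruitment. That section also shows that the current text was written after the decision to close, so new continuation wording could not alter any accrual decision already made.

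**Conclusion.** No change to the plan follows. The 7.4.1 sentence is a dangling cross-reference, a clerical slip that sections 9.2 and 9.4.5 settle. An analyst following the document would take no efficacy look and would report each cohort's response rate with a 95% confidence interval, whether or not the sentence stayed. The power figures and the 14/20 and 12/20 illustrations are correct for a fixed 20 patients.

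The inflation figures, about 7% to 13% for one extra look and 14.0% / 16.4% for a look after each patient from 10 to 20, describe a procedure that the documents do not set out. The conclusion rests on two readings: that 7.4.1 is subordinate to the statistical plan it names, and that accrual closed because of recruitment, as 11.2 indicates. If response data had in fact guided closure, the 0.10 criterion could not be applied at face value. Whether they did is a question for the study report, and rewording this plan would not answer it.
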